# Amendment: Updated Statistical Analysis Plan

## **Trial hypotheses and outcomes**

The objective of this sub-study of the CLASSIC trial is to use the randomisation to restrictive or standard IV fluid therapy to study temporal changes of lactate and time to resolution of hyperlactatemia.

#### **Research questions:**

- 1. Do lactate values differ between the two intervention groups in terms of:
  - a. Differences in time to resolution of hyperlactatemia (defined as plasma lactate <2 mmol/L), ICU discharge and death.
  - b. Temporal changes in lactate concentrations over time (based on all available plasma lactate analyses during the first 72 hours from randomisation).
- 2. Same question as 1.a. above but comparing patients with a highest baseline (= the 3 hours leading up to randomisation) lactate of >4 mmol/L vs ≤4 mmol/L.

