#### Hypotheses:

- 1. Restrictive IV fluid will not significantly affect the time to resolution of hyperlactatemia compared with standard IV fluid.
- 2. Patients with baseline lactate >4mmol/L will not reach resolution of hyperlactatemia faster with standard IV fluid compared with restrictive IV fluid.

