#### Method and design

All available serial time-stamped point-of-care blood gas analyses from patients included in the CLASSIC trial will be retrospectively collected and analysed for the first 72 hours after randomisation or until death or discharge from the ICU, whichever comes first.

The full baseline patient characteristics of the sub-study cohort (age, sex, pre-existing comorbidities (haematological or metastatic cancer, ischemic heart disease, chronic hypertension and long-term dialysis), time from hospital/ICU admission to randomisation, the Simplified Mortality Score for the Intensive Care Unit (SMS-ICU) [1] and predicted 90 day mortality, source of ICU admission, focus of infection, bodyweight, highest plasma lactate, highest dose of norepinephrine, volume of IV fluid 24 hours before randomisation, use of systemic corticosteroids, highest creatinine and use of respiratory support) will be presented in Table 1. Categorical variables will be summarised as N (%) and continuous as median (IQR); if more informative, very skewed continuous variables will be binned and reported as ordinal ones. Cumulative fluid volumes and balances for days 1 through 3 will be presented in Table 2. Outcome data will be presented in Table 3. These data will be collected from the CLASSIC RCT trial database.

We will produce a descriptive graph (Figure 1), depicting medians of lactate values over time with interquartile ranges for the two treatment arms, inspired by figure 1 in the post-hoc analysis of the CLASSIC feasibility trial by Hjortrup et al [2].

Time to resolution of hyperlactatemia will be modelled with a competing risks regression model adjusting for stratification variables (site/centre, hematologic/metastatic malignancy), SMS-ICU Score, focus of infection (urinary tract focus versus other foci), and use of systemic corticosteroids; the same covariates were used in the adjusted analysis of the primary outcome in the large CLASSIC trial [3,4]. Death and discharge will be competing outcomes, and administrative censoring imposed 72 hours after randomisation. The significance levels for the analyses of research questions 1.a and 2 will be 5% and 1%. Figure 2 will visualise the cumulative incidence (%) over the first 72 hours post-randomisation of resolution of shock, discharge and death, stratified by allocation group.

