# Sample size estimate

The estimated sample size will comprise 777 patients consisting of 129 Swedish patients, 599 Danish patients (Capital Region and Region Zealand), and 49 Czech patients.

- Granholm A *et al,* Simplified Mortality Score for the Intensive Care Unit (SMS-ICU): protocol for the development and validation of a bedside clinical prediction rule, BMJ Open 2017;7: e015339. doi: 10.1136/bmjopen-2016-015339
- 2. Hjortrup PB *et al*, Effects of Fluid Restriction on measures of circulatory efficacy in adults with septic shock. Acta Anaesthesiol Scand 2017 Apr;61(4):390-398
- 3. Meyhoff TS *et al*. Restriction of Intravenous Fluid in ICU Patients with Septic Shock (CLASSIC). NEJM 2022 Jun;386(26):2460-2470
- 4. Meyhoff TS et al. Conservative vs liberal fluid therapy in septic shock (CLASSIC) trial-Protocol and statistical analysis plan. Acta Anaesthesiol Scand. 2019 Oct;63(9):1262-1271.

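### The 1% test for research question 2 is not tied to one contrast: the question sets baseline lactate >4 against ≤4 mmol/L, Hypothesis 2 compares the fluid arms within >4 only, and the model has no lactate term

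*SAP*

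**What the plan says.** The objective (SAP, Trial hypotheses and outcomes) is to "use the randomisation to restrictive or standard IV fluid therapy to study temporal changes of lactate and time to resolution of hyperlactatemia". Question 1.a compares the two fluid arms.

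Research questions, item 2, opens "Same question as 1.a. above but" and continues "comparing patients with a highest baseline (= the 3 hours leading up to randomisation) lactate of >4 mmol/L vs ≤4 mmol/L". Both lactate strata are named and set against each other.

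Hypotheses, item 2, reads: "Patients with baseline lactate >4mmol/L will not reach resolution of hyperlactatemia faster with standard IV fluid compared with restrictive IV fluid". This is an arm comparison inside one stratum; the ≤4 stratum does not appear. Item 1, by contrast, covers the whole cohort and has no direction: "Restrictive IV fluid will not significantly affect the time to resolution of hyperlactatemia compared with standard IV fluid".

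Method and design specifies one competing-risks regression for time to resolution. It adjusts for site, haematological or metastatic malignancy, SMS-ICU, focus of infection and systemic corticosteroids, with death and discharge as competing events and censoring at 72 hours. On error rates it says: "The significance levels for the analyses of research questions 1.a and 2 will be 5% and 1" per cent. Read in order, that is 5% for question 1.a and 1% for question 2. Baseline lactate is among the Table 1 variables ("highest plasma lactate, highest dose of norepinephrine") but not among the model covariates.

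**The concern.** A significance level is useful only once the reader knows which coefficient it applies to. For question 2 the SAP sets the level, but its question and its hypothesis point to different coefficients and the model contains no term that would settle the matter.

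The candidates answer different questions. An arm comparison within >4 is a valid randomised subgroup comparison and says whether fluid strategy matters for those patients. It does not say whether the effect there differs from the effect at ≤4. Running the same comparison in each stratum and noting which reaches 1% does not say so either. Only a direct comparison of the two arm effects does.

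If this stays open, any of the three could later be reported as the 1% result for question 2, and a finding within >4 could be presented as showing that the fluid effect depends on baseline lactate.

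**Working it through.** **Side by side**

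| Place in SAP | Patients | Contrast |
|---|---|---|
| Research question 2 | >4 and ≤4 | Question 1.a (arms), set >4 against ≤4 |
| Hypothesis 2 | >4 only | Standard against restrictive |
| Method and design, model | Whole cohort | No lactate stratum, no allocation × lactate term, no subgroup fit |
| Method and design, level | Question 2 | 1%, no coefficient named |

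Three contrasts fit this text:

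1. the arm effect within >4 (Hypothesis 2 as written);
2. the arm effect in each stratum separately (question 1.a done twice);
3. the difference in arm effect between strata (the interaction).

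Under contrast 2 the SAP would also have to say how 1% applies to two tests. The strata share no patients, so two independent tests at 1% each give 1 − 0.99² = 0.0199 overall if neither stratum has an effect.

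**Illustration of how far the contrasts differ**

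The SAP supplies only the cohort size: "The estimated sample size will comprise 777 patients", and 129 + 599 + 49 = 777 reproduces it. Everything else here is assumed: 1:1 arms, 30–50% of patients above 4, 50–80% resolving (equal in both strata), no covariate adjustment, and a normal approximation on the log hazard ratio (HR, standard against restrictive).

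Formulas:
- SE within a stratum = √(4 / events)
- SE of the interaction = √(4 / events in >4 + 4 / events in ≤4)
- two-sided 1% power ≈ Φ(ln 1.5 / SE − 2.576), with ln 1.5 = 0.4055

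Middle case, 40% above 4 and 70% resolving:
- Events: 777 × 0.40 × 0.70 = 217.6 in >4; 777 × 0.60 × 0.70 = 326.3 in ≤4.
- SEs: 0.1356 in >4; 0.1107 in ≤4; 0.1751 for the interaction.
- HR 1.5 in >4 and 1.0 in ≤4, test within >4: Φ(2.990 − 2.576) = 0.66.
- Same effects, interaction test: Φ(2.316 − 2.576) = 0.40.

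Over the whole assumed grid, power is 0.35–0.84 within >4 and 0.23–0.48 for the interaction. If fewer patients resolve above 4 (30–60%, against 70–90% at ≤4), the ranges are 0.19–0.70 and 0.15–0.43.

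**Why separate stratum tests do not settle effect modification**

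Take the middle case with the same HR of 1.5 in both strata, so there is no interaction. Power is 0.661 in >4 and Φ(3.662 − 2.576) = 0.861 in ≤4. The chance that exactly one stratum reaches 1% is 0.661 × (1 − 0.861) + (1 − 0.661) × 0.861 = 0.092 + 0.292 = 0.38. A significant/non-significant split would then be common although the effects are equal. The interaction test would reject at its nominal 0.01.

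**Sidedness**

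The SAP states none for either level. At 1% the critical value is 2.576 two-sided or 2.326 one-sided.

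**The case against.** The strongest reply is that the intent is plain enough. Question 2 is introduced as question 1.a again, question 1.a compares the arms, and the objective relies on randomisation. On that view the model in Method and design carries over, question 1.a is repeated by stratum, and Hypothesis 2 merely states the expectation for the stratum of interest. The question and hypothesis then differ in scope rather than conflict.

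Much of this stands. The SAP does name the model class; what it leaves out is the contrast, or model term, for question 2. A reader might also infer from the wording of question 2 that a non-randomised comparison of high-lactate with low-lactate patients is planned. The opening words and the objective make that unlikely, so the text does not support it. Nor does it establish that question 2 must be an interaction test, since repeating 1.a in each stratum fits as well.

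The reply does not choose among the three contrasts, however. Naming both strata against each other pulls towards a comparison of effects, Hypothesis 2 pulls towards one stratum, and the covariate list has no term for either.

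A reader might also take the directional wording of Hypothesis 2 as a one-sided test. A prose hypothesis does not declare sidedness, two-sided is the usual default, and the SAP is equally silent for the 5% level. This is a minor omission. Finally, the power figures rest on assumptions apart from N = 777; the mismatch does not depend on them.

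**Conclusion.** The point holds in limited form and should be fixed. Question 2, Hypothesis 2 and the 1% level do not define one contrast, and a test within >4, or separate tests by stratum, cannot show that the fluid effect differs between >4 and ≤4 mmol/L. This follows from the text alone.

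Its practical size cannot be derived from the SAP. Under the stated assumptions the contrasts have clearly different power (0.66 against 0.40 in the middle case), so they are not interchangeable; the width of the ranges shows how little the document constrains these figures.

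The scope is a secondary question. A reader might infer that the primary outcome or the overall arm comparison is compromised; neither depends on how question 2 is resolved, and the contrast for question 1.a is clear.

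**What to change.** Choose one contrast and align the research question, the hypothesis and the Method and design section on it.

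- **If question 2 is meant to set >4 against ≤4:** add baseline-lactate stratum and an allocation × stratum interaction to the existing competing-risks model. Test the interaction at 1%, report the arm effect in each stratum with 99% confidence intervals as description only, and reword Hypothesis 2 to match. The downside is low power (illustratively 0.23–0.48, or 0.15–0.43 with unequal resolving, for a ratio of hazard ratios of 1.5), so a non-significant interaction must not be read as showing equal effects.
- **If only the effect within >4 is meant:** reword question 2 to say so, fit the model in that stratum, test the arm effect at 1%, and draw no conclusion about effect modification. The downside is that dependence of the fluid effect on baseline lactate is left unanswered.

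In either case, add a clause stating that the tests are two-sided, or otherwise. The cost is a few sentences and at most two model terms; highest baseline lactate is already to be collected for Table 1.

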#### Hypotheses:

- 1. Restrictive IV fluid will not significantly affect the time to resolution of hyperlactatemia compared with standard IV fluid.
- 2. Patients with baseline lactate >4mmol/L will not reach resolution of hyperlactatemia faster with standard IV fluid compared with restrictive IV fluid.

## **Primary outcome**

Time to first resolution of hyperlactatemia within 72 hours after randomisation.

Resolution of hyperlactatemia is defined as a plasma lactate value <2mmol/L. We will assess the time from randomisation to the first occurrence of a lactate value <2mmol/L irrespective of subsequent changes in the 72 hours after randomisation.

#### Method and design

All available serial time-stamped point-of-care blood gas analyses from patients included in the CLASSIC trial will be retrospectively collected and analysed for the first 72 hours after randomisation or until death or discharge from the ICU, whichever comes first.

The full baseline patient characteristics of the sub-study cohort (age, sex, pre-existing comorbidities (haematological or metastatic cancer, ischemic heart disease, chronic hypertension and long-term dialysis), time from hospital/ICU admission to randomisation, the Simplified Mortality Score for the Intensive Care Unit (SMS-ICU) [1] and predicted 90 day mortality, source of ICU admission, focus of infection, bodyweight, highest plasma lactate, highest dose of norepinephrine, volume of IV fluid 24 hours before randomisation, use of systemic corticosteroids, highest creatinine and use of respiratory support) will be presented in Table 1. Categorical variables will be summarised as N (%) and continuous as median (IQR); if more informative, very skewed continuous variables will be binned and reported as ordinal ones. Cumulative fluid volumes and balances for days 1 through 3 will be presented in Table 2. Outcome data will be presented in Table 3. These data will be collected from the CLASSIC RCT trial database.

We will produce a descriptive graph (Figure 1), depicting medians of lactate values over time with interquartile ranges for the two treatment arms, inspired by figure 1 in the post-hoc analysis of the CLASSIC feasibility trial by Hjortrup et al [2].

Time to resolution of hyperlactatemia will be modelled with a competing risks regression model adjusting for stratification variables (site/centre, hematologic/metastatic malignancy), SMS-ICU Score, focus of infection (urinary tract focus versus other foci), and use of systemic corticosteroids; the same covariates were used in the adjusted analysis of the primary outcome in the large CLASSIC trial [3,4]. Death and discharge will be competing outcomes, and administrative censoring imposed 72 hours after randomisation. The significance levels for the analyses of research questions 1.a and 2 will be 5% and 1%. Figure 2 will visualise the cumulative incidence (%) over the first 72 hours post-randomisation of resolution of shock, discharge and death, stratified by allocation group.

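### Research question 1.b asks whether lactate differs between the arms over 72 hours, but the only output stated for lactate over time is a descriptive graph with no estimate or interval for the arm contrast

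*SAP*

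**What the plan says.** The lead-in to question 1 (SAP, Research questions) is comparative: "Do lactate values differ between the two intervention groups in terms of". Item 1.b completes it with "Temporal changes in lactate concentrations over time (based on all available plasma lactate analyses during the first 72 hours from randomisation".

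In Method and design, the output that matches 1.b is Figure 1: "We will produce a descriptive graph (Figure 1), depicting medians of lactate values over time with interquartile ranges for the two treatment arms". Its format is described only as "inspired by figure 1 in the post-hoc analysis of the CLASSIC feasibility trial". The one regression model in the plan, a competing risks model, is for time to resolution. Figure 2 shows cumulative incidences. Table 3 is to hold outcome data, without further detail.

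The Hypotheses section does not mention the lactate course. Its first item reads "Restrictive IV fluid will not significantly affect the time to resolution of hyperlactatemia compared with standard IV fluid", and the second also concerns resolution. Significance levels are set for questions 1.a and 2 only.

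On the data, "All available serial time-stamped point-of-care blood gas analyses from patients included in the CLASSIC trial will be retrospectively collected", and the series runs "for the first 72 hours after randomisation or until death or discharge from the ICU, whichever comes first".

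**The concern.** A question about whether two arms differ needs an estimate of the difference and a measure of its uncertainty. Differences between medians can be read off Figure 1, but the bars around them describe patients, not the contrast. Readers may take overlapping bars as no difference when the data would show one, or take separated medians as an effect when the gap lies within chance.

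Question 1.a does not fill the gap. The primary outcome stops at the first value below 2 mmol/L, "irrespective of subsequent changes in the 72 hours after randomisation". A later rise, or a different course above the threshold, does not enter it.

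The graph also needs care at later times. Series end at death or ICU discharge, so late medians describe only patients who are still in the ICU and sampled. The SAP does not say whether a patient contributes one value or several to each time window.

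**Working it through.** **Outputs set against question 1.b**

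| Planned output | Subject | Between-arm estimate or interval for lactate over time? |
|---|---|---|
| Competing risks regression | Time to resolution | No |
| Figure 1 | Lactate over time, median and IQR by arm | No |
| Figure 2 | Cumulative incidence | No |
| Table 3 | Outcome data, contents not given | Not stated |

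**The plan's own figure.** Sample size estimate: 129 + 599 + 49 = 777, which agrees with the stated total. The section gives no effect size, SD or power, so there is nothing further to reproduce.

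**Illustration: width of an IQR against width of an interval for the contrast**

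Inputs:
- From the SAP: 777 patients.
- Assumed: 1:1 allocation; one value per patient at a time point; log-normal lactate with equal spread in both arms; log-scale SD of 0.5 to 0.8.
- Number per arm at a time point: 777/2 ≈ 388, with half (194) and a quarter (97) as a range, because the SAP does not give the number sampled at each time.

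Formulas on the log scale:
- IQR width = 1.349 × SD.
- 95% CI width for the difference in log medians = 2 × 1.96 × SD × √(π/2) × √(2/n).

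| n per arm | CI width | IQR width / CI width |
|---|---|---|
| 388 | 0.353 SD | 1.349/0.353 = 3.8 |
| 194 | 0.499 SD | 1.349/0.499 = 2.7 |
| 97 | 0.705 SD | 1.349/0.705 = 1.9 |

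The SD cancels, so these ratios do not depend on it.

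**A 1.2-fold difference (for example medians of 2.0 and 2.4 mmol/L)**

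- Share of the IQR width that overlaps = 1 − ln(1.2)/(1.349 × SD). With SD 0.5: 1 − 0.182/0.675 = 0.73. With SD 0.8: 1 − 0.182/1.079 = 0.83.
- 95% CI = 1.2 divided and multiplied by exp(1.96 × SD × √(π/2) × √(2/n)).
  - 388 per arm: factor 1.09 (SD 0.5) to 1.15 (SD 0.8), so 1.10–1.31 to 1.04–1.38.
  - 194 per arm: factor 1.13 to 1.22, so 1.06–1.36 to 0.98–1.46.

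With 388 per arm the interval excludes 1 although the bars overlap over most of their length. With 194 per arm it excludes 1 at the smaller SD and not at the larger.

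**Identical arms.** The same factors give the 95% range of chance movement in the ratio of medians: 9–15% with 388 per arm, 13–22% with 194 and 19–33% with 97. Some visible separation is therefore expected without any effect.

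**The case against.** The strongest reply is that the plan treats 1.b as descriptive throughout. Figure 1 carries that label, no hypothesis covers the lactate course, and no significance level is assigned to it. Nothing in the SAP says that inference will be drawn from the graph. On this view only a shared lead-in sentence is too strong. This stands in part: a reader might infer that the plan has forgotten a test or an alpha for 1.b, and the documents do not support that. What remains is that the question is still worded as a comparison, and an exploratory comparison also needs an interval.

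Three further points limit the concern.

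- Table 3 is unspecified. The claim must therefore be that Figure 1 is the only output *stated* for lactate over time, not that no other can exist.
- A reader might infer that Figure 1 will pool repeated samples, so that often-sampled patients dominate. The SAP does not say this. It refers to an earlier figure that is not at hand, so the rule is missing detail rather than an error.
- That an IQR is wider than an interval for a contrast is true of any two-arm trial of this size. The figures above rest on assumed inputs and show scale; they do not measure a defect particular to this trial.

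It can also be objected that contrasts among patients still in the ICU are selected on events after randomisation. That is correct. Figure 1 carries the same selection, without numbers to show it.

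**Conclusion.** The point holds as a mismatch between question and output. Question 1.b asks whether the arms differ, and the only output stated for lactate over time gives no estimate or interval for that difference. Question 1.a cannot stand in for it.

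The weight is modest. A reader might infer that the trial's main result is at risk; it is not, because the primary analysis does not depend on Figure 1. The reading of the text needs no assumption. The size (IQR 1.9 to 3.8 times as wide as the interval for the contrast) rests on 1:1 allocation, one log-normal value per patient, equal spread, and 97 to 388 patients sampled per arm.

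**What to change.** Use one value per patient per stated time window. At a few prespecified times (for example 12, 24, 48 and 72 hours), report the between-arm ratio of lactate with a 95% CI among patients in the ICU and sampled. A linear regression of log-lactate on arm, baseline log-lactate and the primary-model covariates gives a ratio of geometric means. Baseline can be the highest value in the 3 hours before randomisation, as research question 2 already defines it. Label the result exploratory, make no significance claim, and print the numbers in the ICU and sampled by arm under Figure 1.

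If a mixed model with an arm-by-time term is preferred, state that under missing at random it extrapolates past death and discharge, and so does not describe lactate while alive and in the ICU.

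Approximate precision at one time point is a factor of exp(1.96 × SD × √(1 − r²) × √(2/n)), with assumed log-SD 0.5 to 0.8 and baseline correlation r 0 to 0.5. This gives 1.06–1.12 with 388 per arm, 1.09–1.17 with 194 and 1.13–1.25 with 97.

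The cost is a few regressions on data already to be collected and one rule for the figure. The contrasts, like Figure 1, are conditional on being alive, in the ICU and sampled, so later ones are not a pure randomised comparison. Informative sampling is not cured.

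If no contrast is wanted, the minimum is to reword 1.b as descriptive and draw no between-arm conclusion from Figure 1.

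### The primary competing-risks model leaves out baseline lactate, although the outcome is lactate itself falling below 2 mmol/L; the test is valid but gives up power that is cheap to recover

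*SAP*

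**What the plan says.** Under Primary outcome, the SAP assesses "the time from randomisation to the first occurrence of a lactate value <2mmol/L", within 72 hours.

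Under Method and design, "Time to resolution of hyperlactatemia will be modelled with a competing risks regression model". That sentence then fixes the covariates, as follows: "adjusting for stratification variables (site/centre, hematologic/metastatic malignancy), SMS-ICU Score, focus of infection (urinary tract focus versus other foci), and use of systemic corticosteroids". The only reason given for this set is that "the same covariates were used in the adjusted analysis of the primary outcome in the large CLASSIC trial". The type of competing-risks model is not named.

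Baseline lactate appears in two other places. Research question 2 is a version of question 1.a "comparing patients with a highest baseline (= the 3 hours leading up to randomisation) lactate" above 4 mmol/L with those at or below it. The Table 1 variables under Method and design include "bodyweight, highest plasma lactate, highest dose of norepinephrine". Neither brings lactate into the model for question 1.a.

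Hypothesis 1 is that restrictive fluid "will not significantly affect the time to resolution of hyperlactatemia". Under Sample size estimate, "The estimated sample size will comprise 777 patients"; this is a count by country, with no effect size, event rate or power.

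**The concern.** The covariates were chosen for a different outcome. When the event is lactate crossing a fixed threshold, the starting level is an obvious candidate for a strong prognostic factor. On the log scale, a patient starting at 8 mmol/L has twice as far to fall to 2 mmol/L as one starting at 4: ln(8/2) = 1.386 against ln(4/2) = 0.693. Leaving a strong prognostic factor out of a hazard model pulls the estimated treatment effect towards the null and lowers power.

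The direction matters because Hypothesis 1 predicts a non-significant result, so avoidable loss of power favours the prediction. The sample is also whatever the participating regions can supply, so the choice of covariates is one of the few ways left to gain precision. The split at 4 mmol/L in research question 2 does nothing for the precision of question 1.a.

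**Working it through.** **The plan's own figure.** 129 + 599 + 49 = 777, which agrees with the SAP. No power is stated, so there is none to reproduce.

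**Inputs from the SAP.** N = 777; the listed covariates; competing events death and discharge; administrative censoring at 72 hours; 5% level for question 1.a (taken as two-sided).

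**Assumed, not in the SAP.** Resolution hazard ratio 1.25 between arms; 78% or 56% of patients resolving; exponential times; 12 site indicators; correlation 0.3 between lactate and SMS-ICU. The strength of lactate is varied: the resolution hazard is divided by exp(b) for each SD of log-lactate.

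**Power simulation.** Every fit contains arm, site, malignancy, SMS-ICU, urinary focus and corticosteroids; the second of each pair adds log-lactate. As the model type is open, both readings were run: Fine-Gray with robust standard errors, and cause-specific Cox with model-based ones. There were 3000 replicates per scenario. Cells show power in % without / with lactate, then the gain in points. Rows are size-adjusted to 5% except those marked *.

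| b | Fine-Gray, 78% | Fine-Gray, 56% | Cause-specific, 78% | Cause-specific, 56% |
|---|---|---|---|---|
| 0 | 66.3 / 66.2 (−0.1) | 54.8 / 54.9 (0.1) | 77.3 / 77.5 (0.2) | 61.5 / 61.3 (−0.2) |
| 0.15* | 64.8 / 65.9 (1.1) | 51.7 / 52.2 (0.5) | 78.0 / 79.2 (1.2) | 61.8 / 62.3 (0.5) |
| 0.3* | 63.6 / 67.1 (3.5) | 50.4 / 52.6 (2.2) | 75.7 / 79.9 (4.2) | 60.5 / 63.7 (3.2) |
| 0.4 | 60.0 / 64.0 (4.0) | 48.5 / 51.2 (2.7) | 69.9 / 75.9 (6.0) | 56.2 / 62.3 (6.1) |
| 0.7 | 50.8 / 62.1 (11.3) | 41.9 / 50.1 (8.2) | 60.4 / 77.8 (17.4) | 48.4 / 63.0 (14.6) |
| 1.0 | 41.3 / 55.7 (14.4) | 35.1 / 46.1 (11.0) | 47.6 / 78.3 (30.7) | 40.0 / 63.2 (23.2) |

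Within a column, rows with and without * are on different scales and should not be compared. Without size adjustment, the Fine-Gray gains are 3.1–5.4 points at b = 0.4, 8.1–12.3 at 0.7 and 13.9–19.0 at 1.0.

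**In patients.** By normal approximation, the share of the sample lost is 1 − [(1.96 + z without) / (1.96 + z with)]², where z is the normal quantile of the power. For Fine-Gray:

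- b = 0.4, 78% resolving: 1 − (2.2133 / 2.3185)² = 0.089, and 0.089 × 777 is about 69 patients. With 56% resolving: 1 − (1.9224 / 1.9901)² = 0.067, about 52.
- b = 0.7, 78% resolving: 1 − (1.9801 / 2.2681)² = 0.238, about 185. With 56% resolving: 1 − (1.7555 / 1.9625)² = 0.200, about 155.

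**Null rejection** (4000 replicates per scenario), Fine-Gray with robust standard errors:

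- Without lactate: 4.8–5.6%.
- With lactate, at b = 0 / 0.4 / 0.7 / 1.0: 5.6 / 5.8 / 5.9 / 6.6% (78% resolving) and 4.8 / 5.2 / 4.9 / 5.9% (56%).
- With lactate and model-based errors instead: up to 8.0% at b = 1.0.

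The cause-specific model with lactate rejects 5.2–5.9%.

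**Where in the range?** Suppose lactate falls log-linearly at a patient-specific rate r unrelated to its start, so that time to resolution is [ln(start) − ln 2] / r, and 30–50% start above 4 mmol/L. The implied b is about 1.2, 0.8, 0.55 and 0.4 when the 90th/10th percentile ratio of r is 3.6, 13, 47 and 168. If baseline is measured with error (log-SD 0.3, 40% above 4 mmol/L), b is 0.8, 0.56 and 0.33 at ratios 3.6, 13 and 168. Fine-Gray gains in these runs are 3–12 points without error (not size-adjusted) and 2–10 with it (size-adjusted).

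**Second simulation.** This used hazard ratio 0.80 (the same size of effect, since 1/0.80 = 1.25), 79–85% resolving, an SMS-ICU-type covariate only, and lactate strength as a hazard ratio per doubling:

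| Per doubling | Cause-specific power, % | Fine-Gray-type power, % |
|---|---|---|
| 1.0 | 83.6 → 83.1 | 70.8 → 70.6 |
| 0.7 | 78.9 → 81.2 | 66.4 → 67.7 |
| 0.5 | 71.3 → 80.4 | 61.5 → 70.4 |
| 0.35 | 58.0 → 77.4 | 49.4 → 64.2 |

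The pattern is the same. Null rejection was 3.9–5.1% without lactate and 4.3–5.9% with it.

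**Missing baselines.** With 10% imputed from baseline covariates (Fine-Gray, 78% resolving, not size-adjusted), power is 60.1 / 64.9, 52.6 / 62.5 and 41.7 / 59.2 at b = 0.4, 0.7 and 1.0.

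**The case against.** The strongest reply is that nothing here is wrong. The covariates are fully specified and a reason is given. The data are collected retrospectively and the parent trial's results are already published, so a set fixed by an earlier protocol guards against choosing covariates after the fact. That is a real merit. It is why this is put as an improvement, and why the present set should be kept as a sensitivity analysis.

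Second, the size is assumed throughout. The effect, the resolving proportion, the number of sites and the strength of lactate are not in the SAP, and the loss runs from nil to 30.7 points. This stands. The starred rows are not size-adjusted, so the adjusted Fine-Gray loss at b = 0.3 could be a little below 2.2 points. The largest cause-specific losses come from exponential times; the threshold model, which is closer to the actual outcome, was run for Fine-Gray only.

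Third, the covariate is the peak over three hours and not the value at randomisation, which weakens its link with the outcome. The measurement-error runs lower the implied strength from 1.2 to 0.8 and from 0.4 to 0.33, but do not remove the gain.

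Fourth, the proposed test is least well calibrated where the gain is largest: 5.9–6.6% null rejection at b = 1.0 even with robust errors. This also stands, but the tabulated gains at b = 0.4 and above are size-adjusted and so do not come from over-rejection.

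Finally, taking a non-significant result as support for Hypothesis 1 is a separate weakness, which adding lactate does not cure.

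**Conclusion.** The point holds, as an inefficiency. The analysis is valid as written, and the accompanying shift in the hazard ratio is partly non-collapsibility and is not counted as bias. Under the assumptions above, a Fine-Gray analysis without lactate loses 0.5–1.1 points of power if lactate is weakly prognostic (b = 0.15), 2.2–4.0 if moderately (0.3–0.4) and 8.2–14.4 if strongly (0.7–1.0). The cause-specific losses are 0.5–1.2, 3.2–6.1 and 14.6–30.7. If lactate is not prognostic, nothing is lost.

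The threshold definition of the outcome makes the weak end less plausible, but that rests on an assumed model of lactate decline. Confidence that there is some loss is good; confidence in its size is moderate. The change is worth making because it costs so little.

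**What to change.** Before the lactate data are analysed, amend Method and design as follows:

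- Add highest baseline lactate, by the three-hour definition in research question 2, to the primary model as a continuous log-transformed covariate.
- State that missing baseline values are imputed from baseline data only, so that no patient is dropped.
- If the model is Fine-Gray, specify robust (sandwich) standard errors.
- Keep the parent-trial covariate set without lactate as a pre-specified sensitivity analysis.

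The cost is one covariate and two sentences. The price in principle is that strict identity with the parent trial's covariates moves from the primary to the sensitivity analysis, with slight over-rejection under Fine-Gray if lactate proves extremely prognostic.
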